- (23) Subject has been treated a) with a scheduled dose of anti-anxiety agents (e.g., benzodiazepines) or sleeping aids (e.g. Ambien or sedative hypnotics) or b) with pain medication other than Non-Steroidal Anti-Inflammatory Drugs (NSAIDS) in the last one month except for procedure related pain management (e.g., dental procedures).
- (24) Has greater than three current criteria for Alcohol or Substance Use Disorder using DSM-V criteria.
- (25) Does not have a period of 48 hours of no alcohol use on TLFB to participate in scanning given the effects of alcohol consumption on the GABA.
- (26) Has a neurologic condition, such as a Traumatic Brain Injury (TBI) with a loss of consciousness of greater than 30 min, that in the opinion of the PI could compromise subject safety or the integrity of the study.
- (27) Has a medical condition that in the opinion of the PI could compromise subject safety or the integrity of the study.
- (28) Subject would not be expected to complete the study including scheduling issues.
- (29) Has an Axis-I diagnosis, other than depression except as listed, that in the opinion of the PI would interfere with the subject's participation in this study.
- (31) Has participated in another research study in the last 3 months that could affect the dependent variables.
- (32) Must have a period of 24 hours of no nicotine use on TLFB to participate in scanning or nicotine use as allowed by CSD&R Project Manager.
- (33) Subject does not agree to study procedures designed to protect against COVID-19 and the requirements of the virtual interventions.

3.3.2.7. Randomization: Group assignments will be conducted using permuted block randomization with varying block sizes. Block sizes will be multiples of the number of treatments and take the allocation ratio into account. For this study with a 1:1 randomization of 2 groups (yoga and walking), block sizes will be 2, 4, and 6. Randomization will be computer generated with each randomization assignment put on a card in numerically labeled envelopes that will be sealed. The envelopes will be opened in sequential order at the time of randomization by a member of the staff that is not blinded to group assignment. Subjects who want more time to think about participation can be randomized within 12 days of the last screening assessment, with the interventions starting within 7 days.

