for certified yoga instructors with Iyengar training who have at least 5 years teaching experience. Instruction in coherent breathing is necessary because the positive effects on sympatho-vagal balance depend not only on the respiratory rate, but also on degree of effort, depth, and muscle relaxation while breathing. Without proper instruction, some inhale too rapidly, overfill their lungs, exhale too forcefully, overuse abdominal muscles, or breathe paradoxically (contracting abdominal muscles while inhaling). Any of these errors could increase sympathetic activation, interfere with parasympathetic activation or even cause hyperventilation. (16) Instructors are needed to observe subject breathing and to monitor and provide corrective feedback.

The COVID-19 pandemic has resulted in all of the yoga instructors providing yoga classes virtually. In order to support social distancing the yoga interventions will be provided virtually through a platform approved by the ISSO officer, such as VA Video Connect. The yoga instructors will teach all yoga interventions virtually. The subjects will be required to attend the randomization, and weeks 4, 8, and 12 interventions at the VABHCS so that equipment can be provided or collect and pre and post intervention data can be collected.

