3.3.2.12. Walking Intervention: The walking intervention was developed and used in Study 2. The literature documents the benefit of physical activity in the treatment of depression, such that a walking group can be considered an active control.(47) For the in-person walking intervention, subjects walk in an indoor circuit with a defined length such that the number of circuits required for a rate of 2.5 miles an hour rate are completed in 60- minutes. Subjects are monitored so that they complete 25% of the required circuits every 15-minutes. The time for the group walking intervention is 60-minutes per group session and the homework is for 15-minutes three times a week, beyond typical walking. The walking group and homework are designed to match the physical activity of the yoga group (i.e., time spent doing yoga postures), not the length of yoga sessions, this results in the walking intervention taking less time than that of the yoga group, with the extra time in the yoga group due to the breathing exercise that does not include group interactions or physical exertion. Study staff will be trained to monitor the intervention and direct subjects to ensure the correct number of laps are completed.

In order for the interventions to be as balanced as possible, the subjects assigned to the interventions will need to come to the VABHCS the same number of times as the subject assigned to the yoga intervention. For the virtual walking sessions, subjects will check in with research staff at the beginning and end of each session by video or telephone. Virtual walking sessions will also include walking at 2.5 miles an hour on a flat surface. During the screening process, subjects will be evaluated for stride length,such that the number of steps to equal 2.5 miles will be calculated. At the randomization session, subjects will be instructed on how to use the pedometer. Subjects will wear a pedometer for each walking session, both in-person and at home, the number of steps for each session will be recorded four times during the intervention and at the end of the homework to document the distance walked. Subjects can provide documentation of the number of steps by photographing the pedometer and sending an email or text or by reporting to the walking intervention monitor during the session.

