3.5. Analysis Plan

3.5.1. Data Management and Analysis Plan: The study statistician and Healthcare Specialist will be responsible under a contract for data management and statistical analysis for the project. The Healthcare team will convert the REDCap shell from an earlier study and provide the monitoring reports, create of the final database. The study statistician will oversee the statistical analysis with the help of the Healthcare Specialist. Descriptive statistics will be generated for baseline data and distributions between the yoga intervention and walking intervention will be compared using two-sample t-tests and chi-square or Fisher's exact tests to assess effectiveness of randomization. Descriptive statistics include means and standard deviations for continuous variables and group sizes and proportions for categorical variables. All analyses will be performed at the $\alpha = 0.05$ level of significance. Should groups have unequal distributions at baseline, relevant variables will be incorporated in subsequent linear models that will be used to examine intervention efficacy. In order to address the study aims of assessing the relative longitudinal change independent variables between yoga intervention and walking intervention groups over time, data will be collected at four time points, pre-randomization, and at weeks 4, 8, and 12. Mixed linear model analyses will be performed focusing on the group x time interaction for the primary effects to be statistically modeled. These analyses will allow for inclusion of data at differing numbers of time points per subject if needed. We will examine different within-subject correlation structures for our interaction model and determine the optimal structure by comparing Akaike information criteria (AIC) values. The correlation structure that yields the lowest AIC will be adopted. Subjects who change antidepressant medications during the study will be included in intent to treat analysis, but will be co-varied for medication changes. Potential cohort effects will be statistically addressed by controlling for group profiles, including group size, breakdown by sex of attendees, instructor, group parameters such as individual or group sessions, and group cohesion/overlap.

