Hypothesis 4. a. Exploratory Concurrent Antidepressants: The yoga group but not the walking group will have a decrease in depressive symptoms regardless of antidepressant treatment at the beginning of the study.

Hypothesis 4. b. Exploratory PTSD Symptoms: If PTSD symptoms are present at screening, there will be a greater decrease in PTSD symptoms in the yoga compared to the walking group as measured by CAPS and PCL-C.

Hypothesis 4. c. Resting State Connectivity will increase over the course of the study with greater increases in the yoga group.

Hypothesis 4. d. Executive Function will increase over the study as measured by the Stroop, Digit Symbol test and fMRI activation.

3.5.2. Power Analysis for Depressive symptoms and Mood Scales: Based on the power analyses below, in order to achieve adequate power for all analyses, n=70 subjects, n=35 in the yoga and n=35 in the walking intervention must complete the interventions. Using Study 4 data in subjects with MDD in the LDG, the repeated measures ANOVA for EIFI scores from screening to the completion of the intervention did not reach statistical significance in the group of n=15 (baseline: 3.1 ± 2.2 and week-12: 3.9 ± 2.7 , $F_{1,13} = 1.097$, $p = 0.31$), a post hoc power analysis was conducted, which determined that the achieved effect size was $f = .281$, with 52% power. Based on this same effect size, an a priori power calculation was conducted, which determined that **n=35** subjects would be needed to detect significant differences for BDI-II, STAI, and EIFI scores from screening to the completion of the intervention, with effect size $f = .281$, with $< = .02$ to account for multiple comparisons, and 81% power. As the power analysis for the EIFI requires the largest number of subjects (n=70), which will be used to determine sample size. In order for 70 subjects to complete the intervention, assuming a 20% drop out, 84 subjects will be randomized.

3.5.3. Power Analysis for GABA: Consistent with our analytic plan for the longitudinal questions at-hand, we can compute the statistical power for Hypothesis II an analysis sample of **n=26** subjects in each of the study groups using the mixed linear model analogue of repeated measures analysis-of-

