A Randomized Control Trial Treating Depression With Yoga and Coherent Breathing Versus Walking in Veterans

NCT03489122

Document Date: 3-20-2017

D.17. Data Management and Analysis Plan: The Data Coordinating Center at the Boston University School of Public Health will provide data management, including the development and maintenance of a REDCap database and the creation of a final database that will be sent to [name] for statistical analysis, using SPSS 23.0. Descriptive statistics will be generated for baseline data and distributions between the yoga intervention and walking intervention will be compared using two-sample t-tests and chi-square or Fisher's exact tests to assess effectiveness of randomization. Descriptive statistics include means and standard deviations for continuous variables and group sizes and proportions for categorical variables. All analyses will be performed at the $\alpha = 0.05$ level of significance. Should groups have unequal distributions at baseline, relevant variables will be incorporated in subsequent linear models that will be used to examine intervention efficacy. In order to address the study aims of assessing the relative longitudinal change in dependent variables between yoga intervention and walking intervention groups over time, data will be collected at four time points, pre-randomization, and at weeks 4, 8, and 12. Mixed linear model analyses will be performed focusing on the group x time interaction for the primary effects to be statistically modeled. These analyses will allow for inclusion of data at differing numbers of time points per subject if needed. We will examine different within-subject correlation structures for our interaction model and determine the optimal structure by comparing Akaike information criteria (AIC) values. The correlation structure that yields the lowest AIC will be adopted. Subjects who change antidepressant medications during the study will be included in intent to treat analysis, but will be co-varied for medication changes. Potential cohort effects will be statistically addressed by controlling for group profiles, including group size, breakdown by sex of attendees, instructor, group parameters such as individual or group sessions, and group cohesion/overlap.

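### The primary group x time model is to be adjusted for instructor and for features of the delivered sessions; these belong outside it, because most arise after randomization and instructor is nested in arm

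*SAP*

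**What the plan says.** SAP D.17 names its target effect: "Mixed linear model analyses will be performed focusing on the group x time interaction for the primary effects to be statistically modeled". On timing it says that "data will be collected at four time points, pre-randomization, and at weeks 4, 8, and 12". The same paragraph handles cohort effects by "controlling for group profiles, including group size, breakdown by sex of attendees, instructor, group parameters such as individual or group sessions, and group cohesion/overlap". Protocol 3.5.1 (Data Management and Analysis Plan) keeps the rule: "Potential cohort effects will be statistically addressed by controlling for group profiles". Neither document says whether these terms are fixed or random, main effects or crossed with time, or how a participant who attends many sessions is to be coded.

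Delivery is described in Protocol 3.3.2. For yoga (3.3.2.11), certified teachers with Iyengar training lead the classes: "The yoga instructors will teach all yoga interventions virtually". For walking (3.3.2.12), the leaders are study staff: "Study staff will be trained to monitor the intervention and direct subjects to ensure the correct number of laps are completed". Section 3.3.2.12.1 treats yoga instructors and walking monitors as two separate roles for fidelity assessment, and offers four group sessions a week in each arm. Section 3.3.2.11 lets missed yoga classes be made up.

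**The concern.** There are two distinct problems.

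**Variables that arise after assignment.** How many people attend a session, their sex mix, whether it runs for one person or several, and how cohesive the group becomes are all settled after randomization. If group contact is part of how yoga or walking helps, these features lie on the path from assignment to outcome. D.17 speaks of an intent-to-treat analysis, and conditioning on such features answers a different question.

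**Instructor nested in arm.** No section has one person leading both arms. A fixed instructor term therefore shares information with the arm indicator. Depending on coding, it either does nothing about instructor differences in change, or it leaves the printed arm x time coefficient without a unique value.

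At stake is whether the reported group x time effect is the effect of assignment to yoga rather than walking, and whether two analysts following the same sentence would report the same quantity.

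**Working it through.** **Inputs from the documents.** Allocation is 1:1 (Protocol 3.3.2.7: "For this study with a 1:1 randomization of 2 groups (yoga and walking), block sizes will be 2, 4, and 6"). Completers are 35 per arm (3.5.2: "n=35 in the yoga and n=35 in the walking intervention must complete the interventions"). There are four time points (D.17). **Assumed**, because no counts are given: 3 yoga instructors and 2 walking monitors for the rank check; 2 to 4 yoga instructors and intraclass correlations (ICC) of 0.01 to 0.10 for the precision check.

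**1. The plan's own group x time power.** Protocol 3.5.3 gives 26 per arm, SD 0.06, correlation 0.65, yoga means 0.28, 0.285, 0.32 and walking means of 0.28 throughout.
- Arm differences are 0, 0.005, 0.04, with mean 0.015. Deviations are -0.015, -0.010, 0.025, and half of each goes to each arm.
- Sum of squared interaction effects = 2 x (0.0075² + 0.005² + 0.0125²) = 0.000475.
- Noncentrality = 26 x 0.000475 / (0.0036 x 0.35) = 9.80. With 2 and 100 degrees of freedom, power is 79.5%, against the stated 80%.
- At correlation 0.70: 0.01235 / (0.0036 x 0.30) = 11.44, power 85.6%, against the stated 85%.

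Both figures reproduce. The calculation contains no instructor or session covariate.

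**2. Instructor as a fixed effect.** The base design has an intercept, arm, 3 visits and 3 arm x visit terms: 8 columns, rank 8.

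| Instructor coding | Columns | Rank | Arm x week-12 coefficient | Change contrast averaged over each arm's instructors |
|---|---|---|---|---|
| none | 8 | 8 | estimable | estimable |
| main effect | 8 + 5 = 13 | 11 | estimable | estimable |
| main effect and x time | 13 + 15 = 28 | 20 | not estimable | estimable |
| time-varying, none at baseline | 8 + 5 = 13 | 11 | not estimable | estimable |

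The aliasing follows from exact nesting, so it does not depend on the assumed 3 and 2. Replacing single instructors by shares of attended sessions gives the same ranks.

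In one simulated data set, the main-effect version left the complete-data estimate at -5.056 (SE 1.691), identical to the model without instructor. With 20% dropout the estimate moved from -5.80 to -5.84 (SE 1.7945 to 1.7951). In the two aliased codings, with complete simulated data, the averaged contrast equalled the plain yoga-minus-walking difference in change.

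**3. Features of delivered sessions.** With complete data, a linear model that includes a feature and its interaction with time returns

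adjusted difference in change = unadjusted difference - (fitted coefficient of the feature on change) x (arm difference in the feature's mean).

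The shift is zero only if the arms have the same mean for that feature or the fitted coefficient is zero. The documents give neither quantity, so the shift cannot be sized. As an illustration, suppose 10% of yoga and 50% of walking participants have individual sessions. The design is then full rank (12 of 12) and group x time is estimable. The simulated estimate nevertheless went from -5.06 to -6.89, and its SE from 1.69 to 1.87. No format effect was built into those data, so this movement is chance sharing between format and arm. It shows sensitivity and is not an estimate of bias.

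**4. Precision with a random instructor effect in the yoga arm.** Let m = 35/J for J instructors, design effect = 1 + (m - 1) x ICC, and SE ratio = √[(design effect + 1)/2]. This assumes one instructor per participant and no clustering in the walking arm.
- J = 4, ICC 0.01: m = 8.75, design effect 1.0775, SE ratio 1.019.
- J = 3, ICC 0.05: m = 11.67, design effect 1.533, SE ratio 1.125.
- J = 2, ICC 0.10: m = 17.5, design effect 2.65, SE ratio 1.351.

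**The case against.** The strongest reply is that the sentence says only that these features will be controlled for, inside a mixed model. A random instructor effect would satisfy it and keeps group x time estimable. Even with fixed instructor x time terms, the yoga-walking difference in change averaged over each arm's instructors can still be recovered. That stands. A reader might infer that following the plan makes the yoga effect inestimable. The documents do not support this: only the raw coefficient under particular fixed codings is lost.

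A reader might also infer that individual versus group format simply restates the arm, since virtual walking (3.3.2.12) is described through check-ins at the start and end. The documents do not show that either. Sections 3.3.2.12.1 and 4.6.1.7 describe both arms as group-delivered, and 4.6.1.17 makes the interventions virtual without distinguishing the arms. D.17 is dated 2017, before that change. Thin attendance could also produce one-person sessions in either arm. At 25 randomized a year (4.5.2.9), 25 x 12/52 = 5.8 are in treatment at once, or 2.9 per arm. Two of four weekly sessions each gives 2.9 x 2/4 = 1.4 attendees per session. With even accrual, full attendance and Poisson counts (all assumed), about 45% of occupied sessions would have one attendee.

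Finally, group size, sex mix and cohesion are untouched by the rank argument, and no harm from adjusting for them has been quantified. Both statements are true. But the objection to those variables is that they arise after assignment, which does not depend on collinearity.

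**Conclusion.** The point holds in this form. The primary model is told to condition on features of delivery that arise after randomization, which can shift group x time away from the effect of assignment. It is also told to condition on instructor, which is nested in arm and, as a fixed effect, is either uninformative for group x time or aliases the arm x time coefficient. The plan also gives no rule for assigning one instructor, group size or cohesion value to someone who may attend several sessions with different leaders.

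The direction and size of any shift are unknown, because they depend on arm differences and associations that the documents do not give. The nesting conclusion rests on the described roles and on nobody leading both arms in practice. The 2% to 35% range for the standard error rests on the assumed ICCs and instructor counts. No stated sample size or power figure changes. The sentence should be corrected before the analysis is run.

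**What to change.** In SAP D.17 and Protocol 3.5.1, remove the group-profile covariates from the primary model, so that the primary estimate is group x time without adjustment for delivery.

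Prespecify one sensitivity analysis with instructor as a random effect on change, nested within arm, weighted by the share of attended sessions that each person led. This needs the session leader's name added to the attendance sheets already planned in Protocol 3.3.2.10. Keep it as a sensitivity analysis: with few instructors the variance component will be poorly estimated.

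Report group size, sex mix of attendees, session format and cohesion descriptively by arm, or in exploratory models within each arm.

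The cost is a change of wording, one extra field on the attendance record, a little more analysis work, and a wider interval in the sensitivity analysis.
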